3.2 Study Endpoints

3.2.1 Primary Endpoint

The primary endpoint is the percentage of patients with a primary diagnosis of OPC, EC, or VVC who achieve Clinical Responder status after 14 days of treatment at the highest titrated CAMB dosage per patient (Target Dosage). Clinical Responder will be defined as patients who achieve Complete Clinical Cure or Clinical Improvement. The Clinical Response evaluation for each specific diagnosis of mucocutaneous candidiasis is described below:

OPC:

- Clinical Cure: Absence of plaques or ulcers and absent or minimal symptoms.
- Clinical Improvement: Partial resolution (≥ 50%) of pretreatment (Baseline) signs and symptoms.
- Clinical Failure: No improvement (< 50%) or worsening of pretreatment (Baseline) signs or symptoms.
- Not evaluable: Subject not evaluable due to lack of follow-up visits.

EC: Patients will undergo a research-indicated upper endoscopy to evaluate for esophageal candidiasis at the end of treatment or within 4 weeks of clinical improvement. Clinical cure will only be used for those patients who undergo this

endoscopy. If more than three patients decline to undergo this procedure, then this endpoint will be re-assessed.

- Clinical Cure: Absence of plaques or ulcers on endoscopy and absent or minimal symptoms.
- Clinical Improvement: Partial resolution (≥ 50%) of pretreatment (Baseline) symptoms or signs.
- Clinical Failure: No improvement (< 50%) or worsening of pretreatment (Baseline) signs or symptoms.
- Not evaluable: Subject not evaluable due to lack of follow-up visits.

VVC:

- Clinical Cure: Absence of signs and symptoms of vaginitis.
- Clinical Improvement: Reduction of ≥50% of the clinical severity score from Baseline.
- Clinical Failure: Worsening of symptoms or reduction in clinical score of <50% from Baseline.
- Not evaluable: Subject not evaluable due to lack of follow-up visits.

3.2.2 Secondary Endpoints

- 1. Plasma, urine, and salivary single-dose and steady-state PK parameters and disposition of oral CAMB.
- 2. Dose linearity/proportionality of oral CAMB with titration.
- 3. Clinical Responder status after 28 days at the Target Dosage.
- 4. Clinical Responder status after 14 days at each dosage level.
- 5. Mycological response after treatment for 14 days and 28 day with the Target Dosage.
- 6. Mycological response after treatment with each dosage level for 14 days.
- 7. Rate of treatment-limiting toxicity.
- Rate of clinical relapse. Clinical relapse will be defined as a reoccurrence of clinical signs and symptoms after being sign and symptom free for 1 week.
- 9. Incidence of nephrotoxicity defined as an increase of more than 100% of

baseline serum creatinine.

- 10. Incidence of hypokalemia, defined as serum potassium ≤ 3 mmol/L during or within 3 weeks of completing treatment.
- 11. Incidence of AEs (see Section 11)
- 12. Clinical Responder status after 14 days of treatment at the Target Dosage per patient of a secondary, less severe candida infection. Clinical Responder will be defined as patients who achieve Complete Clinical Cure or Clinical Improvement.

3.2.3 Exploratory Endpoints

- 1. Stool and vaginal secretion single-dose and steady-state PK parameters and disposition of oral CAMB.
- 2. To assess clinical response in those patients with a concomitant diagnosis of OMC.
- 3. Long-term (up to 60 months) safety and efficacy response.

4 Study Population

4.1 Rationale for Subject Selection

We will enroll patients with immunodeficiencies that result in recurrent or chronic mucocutaneous candidiasis, who are refractory or intolerant to standard non-intravenous therapies. The underlying diseases we expect these patients to have include, but are not limited to: STAT3 deficient Hyper IgE syndrome, gain of function STAT1 mutations, APECED, and thymoma with autoantibodies with IL-17/IL-22 pathway. If a patient has multiple *Candida* diagnoses, for example OPC and VVC or EC and VVC, the diagnosis that is more severe will be documented as the primary diagnosis and used in the primary endpoint analysis. However, all diagnoses will be evaluated and included in the secondary analysis.

Patients will be co-enrolled on 1 of the following NIAID protocols:

- 00-I-0159, Natural History, Management, and Genetics of the Hyperimmunoglobulin E Recurrent Infection Syndrome (HIES)
- 93-I-0119, Detection and Characterization of Host Defense Defects
- 07-I-0033, Screening Protocol for Detection and Characterization of

- Infections and Infection Susceptibility
- 11-I-0187, The Natural History, Immunologic Correlates and Genetic Defects in Patients with Mucocutaneous and Invasive Fungal Infections
- 01-I-0202, Natural History, Genetics, Phenotype and Treatment of Mycobacterial Infections

We hope to enroll a minimum of 16 patients with OPC, EC, and/or VVC.

4.2 Patient Inclusion Criteria

- Age 18-75 years
- Patients must have a clinical diagnosis of at least one of the following:
 - Persistent OPC for greater than or equal to 5-days documented on at least one occasion by KOH or fungal stain and confirmed by mycological culture to be azole resistant within the previous 6 months and/or intolerance to standard non-intravenous therapies or lack of improvement or worsening of OPC after receipt of appropriately dosed oral azole therapy.
 - EC associated with clinical symptoms of retrosternal pain, odynophagia, and/or pain with swallowing and documented by esophageal biopsy or visualization with culture documenting azole resistance within the previous 6 months and/or intolerance to standard non-intravenous therapies or lack of improvement or worsening of EC after appropriately dosed azole therapy.
 - Persistent VVC for greater than or equal to 5-days as documented by presence of vaginal symptoms and a positive wet mount showing *Candida* structures and confirmed by a vaginal culture positive for *Candida* with azole resistance within the previous 6 months and/or intolerance to standard non-intravenous therapies or lack of improvement or worsening of VVC after receipt of appropriately dosed azole therapy.
- Patient is expected to survive for ≥ 6 months.
- Willing to have samples stored for future research.
- Agree to use highly effective contraception (see below).

Contraception: Because the effects of CAMB on the developing human fetus are unknown, sexually active patients of childbearing potential must agree to Page 22 of 101

use highly effective contraception as outlined below before study entry and for the duration of study participation. Females of childbearing potential must have a negative pregnancy test result before receiving CAMB. During the course of the study, if a patient becomes pregnant or suspects they are pregnant, then they should inform the study staff and their primary care physician immediately. Acceptable forms of contraception are:

- Intrauterine device (IUD) or equivalent.
- Hormonal contraceptives (eg, consistent, timely and continuous use of contraceptive pill, patch, ring, implant, or injection that has reached full efficacy prior to dosing). If the patient uses contraceptive pill, patch, or ring, then a barrier method (eg, male/female condom, cap, or diaphragm plus spermicide) must also be used at the time of potentially reproductive sexual activity.
- Be in a stable, long-term monogamous relationship, per PI
 assessment, with a partner that does not pose any potential pregnancy
 risk, eg, has undergone a vasectomy at least 6 months prior to first
 dose of study agent or is of the same sex as the patient.
- Have had a hysterectomy and/or a bilateral tubal ligation or both ovaries removed

4.3 Patient Exclusion Criteria

- Allergy to any AMB product or any component of CAMB (eg, phosphatidylserine)
- Have evidence of systemic fungal infections requiring intravenous antifungal therapy
- Pregnant or nursing women, and women intending to become pregnant during the study period
- Had a concomitant medical condition that could interfere with study drug evaluation or that is a contraindication to the proposed investigational treatment based upon known agent safety profile or toxicities.
- Had any of the following laboratory abnormalities at the screening visit:
 - Alanine Transaminase (ALT), Aspartate Transaminase (AST) and Alkaline phosphatase (ALP) >2.5 times the upper limit of normal (ULN).

- Total bilirubin level > 2.5 times the ULN
- Serum creatinine level > 2 times the ULN
- o Absolute neutrophil count less than 500 cells/µL
- Potassium level <3.5 mmol/L
- Exposure to any investigational agent within 4 weeks prior to Day 0 (Baseline).
- Current or recent history (past 12 months) of drug or alcohol abuse.
- Use of intravenous AMB products within 1-week of start of study drug administration
- Use of non-intravenous AMB products (such as oral AMB swishes)
 within 72 hours prior to start of study drug administration
- Any other condition the investigator believes would interfere with the
 patient's ability to provide informed consent, comply with study
 instructions, or which might confound the interpretation of the study
 results or put the subject at undue risk.

Co-enrollment Guidelines:

Co-enrollment in other trials is restricted, other than enrollment on observational studies. Consideration for co-enrollment in trials evaluating the use of a licensed medication will require the approval of Principal Investigator and Sponsor. Study staff should be notified of co-enrollment as it may require the approval of primary investigator.

4.4 Justification for Exclusion of Special Populations

Exclusion of Women

- Pregnancy: Pregnant women are excluded from this study because the
 effects of CAMB on the developing human fetus are unknown, and there is
 the potential for teratogenic or abortifacient effects.
- **Breastfeeding:** Patients who are breastfeeding should cease when being treated with CAMB because of the potential risk for AEs in nursing infants.

Exclusion of Children

Children are not eligible for this study because this is an investigational study with very limited experience in humans regarding safety and appropriate dosing.

We hope that the results of this study will then allow further study including in pediatric patients.

Exclusion of Adults Lacking Capacity to Provide Consent

If participants permanently lose the ability to provide ongoing consent subsequent to giving initial consent, they will be withdrawn from the study (section 11.9).

5 Study Agent/Interventions

5.1 Disposition and Dispensation

Study agent will be distributed via the NIH Pharmacy according to standard pharmacy procedures.

5.1.1 Study Drug Packaging and Labeling

The CAMB will be packaged into Nalgene[™] amber PETG 125-mL square bottles with HDPE closures. The corresponding labels are:

Protocol: MB-70004
Subject ID: ______
Investigator Phone Number:

Encochleated Amphotericin B Suspension (CAMB)

For Oral Use

5 mg/mL Amphotericin B

Lot#: XXXXXXXXX*
Contents: XXX mL

Take as directed by Study Investigator

Shake well before use.

Store refrigerated at 2-8° C. Protect from the light.

Caution: New Drug – Limited by Federal Law to Investigational Use.

Matinas BioPharma Nanotechnologies, Inc. Bedminster, NJ

Patients will be supplied with measuring tools (eg, dispensing cups or syringes) to take home and use for study drug administration and will be instructed on how Page 25 of 101

^{*}Actual values will be listed on Study Drug label.

to use them.

5.2 Study Agent Storage and Stability

5.2.1 Study Drug Storage

All study drug will be stored in a locked area. The area will be free of environmental extremes and with a limited access. Study drug will be kept refrigerated at 2°C to 8°C. The site will maintain records of storage temperature and make them available for Sponsor review.

Patients will be instructed to store study drug in a refrigerator at 2°C to 8°C (36°F-46°F). In order to travel with study drug, patients will be provided a cooler bag and freezer pack to maintain temperature.

5.3 Description, Preparation, and Administration of Study Drug Product

5.3.1 Description

CAMB is a yellow-to-orange suspension that is homogenous upon shaking. It should be stored between 2°C and 8°C. CAMB is light-sensitive and should be stored away from light.⁵ However, exposure of < 4 hours to fluorescent light and excursions of up to 24 hours at room temperature are acceptable. In this study, CAMB was initially provided at a concentration of 5 mg/mL and administered at up to 3 strengths: 100, 200, and 400 mg.

After May 31, 2020, the company has ceased production of the 5mg/mL concentration and move to the higher concentrated formulation of 20mg/mL.

Preparation, Dosing and Administration

The study drug will be provided as an oral suspension. Patients will take the study drug twice per day to reach the total daily dose. Prior to administration, the study drug container will be shaken, the required quantity poured into a dispensing cup, and the remainder of the study drug returned to refrigerated storage. Patients with OPC and/or EC will be asked to swish the suspension in their mouths before swallowing and then refrain from eating or drinking for 30 minutes post-dose. Patients with VVC and/or OMC will be asked to drink suspension without swishing. CAMB is provided at a single concentration

(20 mg/mL). Patients will be instructed to dispense the appropriate volume of solution (5,10 or 20 mL) to reach the target dose, according to the following table:

Total Daily Dose (mg/day)	Single Dose (mg/dose)	Single Dose Volume, 5mg/mL concentration (mL)	Single Dose Volume, 20mg/mL concentrations (mL)
200	100	20	5
400	200	40	10
800	400	80	20

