1.1 Background Information

1.1.1 Description of the StudyAgent

Cochleate oral amphotericin B (CAMB) is a lipid-crystal, nano-particle formulation designed for targeted oral delivery of the antifungal drug amphotericin B (AMB). CAMB is a spiral-shaped phospholipid-cation precipitate that is primarily made up of phosphatidylserine — a naturally occurring phospholipid with a designation of generally recognized as safe (GRAS) from the FDA — and calcium. These multilayer cochleates are comprised of a solid lipid bilayer sheet, rolled into a spiral, with no internal aqueous space. This structure provides protection against degradation, which allows the inner structure to remain intact even after exposure to unfavorable environments (eg, low pH in the stomach), whilst providing the systemic delivery of AMB.

Historically, AMB has been considered the "gold standard" in antifungal treatments due to its broad spectrum of activity and lack of emergence of resistance. However, the use of AMB and its derivatives is limited by side effects, including nephrotoxicity, anemia and infusion related reactions. AMB disrupts the fungal cell wall via its high-affinity binding to ergosterol. The transmembrane channels that form as a result of this binding cause potassium to leak from the cell, thus initiating a lipid peroxidation cascade that causes irreversible damage to the cell.

CAMB demonstrates antifungal activity when administered orally. The efficacy is comparable to AMB but demonstrates reduced toxicity in animal models.

The sponsor changed the concentration of the study drug to a more concentrated formulation of 20mg/ml from the original concentration of 5mg/ml after participants in this study were on the extension phase. A 27.5 mg/mL concentration has been tested in a study of CAMB in Cryptococcal meningitis in 37 individuals and found to be well tolerated up to doses of 2.0grams daily. Due to viscosity concerns, however, the concentration was then changed to 20mg/ml. The dosing change has been submitted to the FDA and no concerns were reported.

After May 2020, the company will cease production of the 5mg/mL Page 11 of 101

concentration and move to the higher concentration of 20mg/mL. The transition to the 20mg/ml concentrate will be implemented once the 5mg/ml study drug supply is dispensed and fully used by the subjects in the trial.

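### The protocol's statements of drug strength conflict: the only label text reads 5 mg/mL, while the dosing text says a single 20 mg/mL product is supplied.

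*Combined protocol and SAP*

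**What the plan says.** Four places in the protocol describe the strength of the oral suspension.

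- **Section 5.1.1 (packaging and labeling)** gives one label text. Its strength line is "5 mg/mL Amphotericin B". A footnote says "Actual values will be listed on Study Drug label", but in the text as supplied its asterisk is on the lot-number line. No second label text is given.
- **Section 5.3.1 (description, preparation, dosing and administration)** gives the history: "In this study, CAMB was initially provided at a concentration of 5 mg/mL". It then reports that production of that strength stopped after 31 May 2020. The dosing paragraph says "CAMB is provided at a single concentration", with 20 mg/mL in parentheses, and continues "Patients will be instructed to dispense the appropriate volume of solution (5,10 or 20 mL) to reach the target dose". The table directly below has one volume column for 5 mg/mL and another for 20 mg/mL.
- **Section 1.1.1 (study agent)** says the sponsor changed the strength after participants were in the extension phase, and puts the changeover in the future: "The transition to the 20mg/ml concentrate will be implemented once the 5mg/ml study drug supply is dispensed and fully used".
- **Section 1.1.3 (clinical studies)** gives the highest single dose in this study as 400 mg and equates it with 80 mL.

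The page footers identify the text as Version 17.0, dated May 2021.

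**The concern.** These statements cannot all describe the same bottle. Someone working from sections 5.1.1 and 1.1.3 works at 5 mg/mL. Someone working from the dosing paragraph of section 5.3.1 works at 20 mg/mL. The conflict lies in the current operative text and not in a record of past changes.

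It matters because patients measure their own doses at home with cups or syringes (sections 5.1.1 and 5.3.1). In the extension the investigator may also change the daily dosage between 200 and 800 mg (section 6.6), so a volume can change for two unrelated reasons. One volume, 20 mL, appears in both columns of the table for different doses, so the volume alone does not reveal a mix-up.

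Two things are at stake: the safety of extension participants, and whether the long-term safety and efficacy data (exploratory, section 3.2.3) can be tied to the dose actually taken. Sections 5.3.4 and 5.4 provide for returned bottles, medication logs and accountability records, but neither names concentration as an item to record. A logged or returned volume becomes milligrams only if the strength is known.

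**Working it through.** **Inputs.** Strengths of 5 and 20 mg/mL (sections 1.1.1, 5.1.1, 5.3.1); single doses of 100, 200 and 400 mg, taken twice daily (section 5.3.1 table); 400 mg given as 80 mL (section 1.1.3).

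**Step 1: reproduce the plan's table.** Volume = dose / concentration.

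| Single dose (mg) | At 5 mg/mL | At 20 mg/mL |
|---|---|---|
| 100 | 100/5 = 20 mL | 100/20 = 5 mL |
| 200 | 200/5 = 40 mL | 200/20 = 10 mL |
| 400 | 400/5 = 80 mL | 400/20 = 20 mL |

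All six volumes agree with the table, so the table itself contains no error.

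**Step 2: match each statement to a strength.**

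- The 5, 10 or 20 mL instruction in section 5.3.1 fits the three doses only at 20 mg/mL.
- The 80 mL in section 1.1.3 fits 400 mg only at 5 mg/mL (80 × 5 = 400).
- The label text in section 5.1.1 fits only 5 mg/mL.
- Section 1.1.1 allows either strength, one after the other.

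**Step 3: size of a mislabelled strength.** Ratio = 20/5 = 4. A 20 mg/mL bottle carrying the section 5.1.1 text would state a quarter of its true strength.

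**Step 4: what a mix-up would deliver, if one happened.** Dose = volume × concentration. These are hypothetical worst cases; the documents give no rate for such errors.

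| Mix-up | Volumes (mL) | Per dose (mg) | Per day, twice daily (mg) |
|---|---|---|---|
| 5 mg/mL volume drawn from a 20 mg/mL bottle | 20 / 40 / 80 | 400 / 800 / 1,600 | 800 / 1,600 / 3,200 |
| 20 mg/mL volume drawn from a 5 mg/mL bottle | 5 / 10 / 20 | 25 / 50 / 100 | 50 / 100 / 200 |

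The intended figures are 100 / 200 / 400 mg per dose and 200 / 400 / 800 mg per day. The factor is 4 in either direction.

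**Step 5: reach into the primary analysis.** Section 13.3.1 calls the drug promising if 3 or more of 16 patients improve. The binomial calculation gives P(X ≥ 3) = 0.0429 at a true rate of 5% and 0.803 at 25%, in line with the stated 0.043 and 0.8. Drug strength does not enter that calculation. The primary endpoint is read after 14 days at the Target Dosage, and section 1.1.1 places the change of strength after participants had reached the extension.

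**The case against.** The strongest reply is that this is incomplete updating after an amendment, with little behind it.

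- **The switch is sequential.** Section 1.1.1 starts the new strength only when the old one is used up, and section 5.3.1 says the old one is no longer made. The single-concentration sentence can then be read as the current state and the 5 mg/mL column as history. This stands in part: a reader might infer that patients were meant to hold both strengths at once, and the documents do not support that. It does not explain why section 1.1.1 still puts the changeover in the future, or why no 20 mg/mL label text exists.
- **No one is told to take a wrong volume.** The table is correct, its columns are headed by strength, and the label gives no volume and leaves dosing to the investigator's direction. This stands. A reader might infer that the protocol instructs a four-fold dose; it does not.
- **The label is a template.** It has placeholders, and its footnote speaks of actual values. This stands only in part: the strength is printed as a fixed figure and the asterisk is on the lot line. A reader might infer that 20 mg/mL bottles were in fact labelled 5 mg/mL; the documents do not say what was printed.
- **Tracing is largely in place.** Lot numbers, returned bottles, logs and pharmacy accountability records exist, and a lot number should usually lead back to a strength. This stands, and it makes the remedy smaller. The link from lot to strength is nowhere stated.
- **The analytic reach is small.** Long-term outcomes are exploratory, and sections 13.3.1 to 13.3.3 specify no dose-response analysis for the extension. This stands for the statistics but does not answer the safety point.

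**Conclusion.** The point holds as a conflict in a stated product specification. Sections 5.1.1 and 1.1.3 give or imply 5 mg/mL, the dosing paragraph of section 5.3.1 gives 20 mg/mL, and section 1.1.1 treats the changeover as pending. As written, the protocol has no label text for the strength it says is supplied, and following section 5.1.1 literally would misstate that strength by a factor of 4.

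The dose figures of up to 1,600 mg and down to 25 mg per dose show what a mix-up could do; they are neither an instructed dose nor an expected effect. The consequence is confined to safety in the extension and the exploratory long-term data. A reader might infer that the primary result is compromised. The documents do not support that, on the assumption, taken from section 1.1.1, that the dosing leading to the primary assessment was all at the original strength.

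The point is worth acting on because patients measure doses at home and the correction costs almost nothing. No view is taken on which concentration or dose is right.

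**What to change.** 1. Reconcile sections 1.1.1, 1.1.3, 5.1.1 and 5.3.1 so that they give one consistent account of strength and volume.
2. In section 5.1.1, make the label text state the strength actually in each bottle, with a text for each strength used in the study.
3. State which concentration applies to which supply period, so that the single-concentration sentence and the two-column table can be read together.
4. Make the concentration of each dispensed supply traceable in the existing accountability record, either by a stated link from lot number to strength or by an explicit field, so that extension exposure can be computed in milligrams.

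The cost is protocol and label wording plus at most one field in the dispensing record. Sample size, visits and the primary analysis do not change.
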